- Patients who have planned a cardiovascular, hepatic or other solid organs surgery and polytrauma patients with injuries of blood vessels, parenchymal organs, lungs qualified for elective surgery
- Patients planned to have at least one TachoSil matrix applied (intraoperatively) and without the plan of application of any other products for local haemostasis at the place of TachoSil application will be qualified for the study.

Exclusion Criteria

The following individuals are not eligible to participate:

- they have known, recognized earlier congenital disorders of haemostasis such as haemophilia type A, B,C, Marfan syndrome, Rendu-Osler-Weber disease, congenital thrombocytopathies, e.g. Glanzmann's thrombasthenia, von Willebrand disease type 1,2,3, Fanconi's anaemia.
- they have experienced severe coagulopathy defined as: INR > 2.0 , platelet count (PLT) $< 50\ 000 / \text{mm}^3$; APTT > 60 seconds in the period from 7 days before to the day of surgery.
- they are hypersensitive to the active substance(s) or to any of the product excipients.

PasTel

- female patients of childbearing potential: they are pregnant or want to become pregnant or those who do not use sufficient methods of contraception such as contraceptive implant, intrauterine coil and oral hormonal contraception.
- The patient who, in the investigator's opinion, presents a known risk of being lost to follow-up during the 36-month follow-up period, based on the screening assessment.

Variables

The following core data elements are to be included in the study database: demographic data, underlying disease/type of surgery, co-morbidities, treatment-related data, relevant concomitant therapies, vital signs and laboratory values routinely performed by the site (such as blood count, C-reactive protein [CRP], International Normalized Ratio[INR], Activated Partial Thromboplastin Time [APTT], adverse events of special interest (AESIs) and other adverse events recorded during perioperative period and follow-up data.

Data sources

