10. RESEARCH METHODS

10.1 STUDY DESIGN

This is a prospective, multicentre, non-interventional, uncontrolled, observational, post-authorization cohort study aimed at investigating the short- and long-term safety of TachoSil application.

The study will enrol patients undergoing cardiovascular, hepatic or other solid organs surgery, as well as those with injuries of blood vessels, parenchymal organs, lungs requiring the use of drugs for local haemostasis, tissue sealing, and suture support in vascular surgery where standard techniques are insufficient and where TachoSil was used as a secondary haemostatic treatment. The cohort will include patients identified by participating investigators (prospective enrolment). Patients who meet specified inclusion/exclusion criteria and their legal representatives will receive comprehensive information about the study orally and in written form, tailored to their understanding. The investigator will obtain their voluntary, personally signed, and dated informed consent before collecting any study-related information.

Short-term safety data, including adverse events (AEs) and adverse events of special interest (AESIs), will be collected prospectively from the time of informed consent signature, during hospital stay, and until hospital discharge. Time to onset (TTO), duration, severity, outcome, treatment and relatedness to TachoSil will be analyzed for reported AEs and AESI.

All enrolled patients will be followed for up to 36 months after surgery to monitor long-term treatment-related events and their clinically significant consequences.

To minimize stress for patients and caregivers associated with the study and the surgical intervention itself, the number and frequency of follow-up visits during the observation period will align with the routine follow-up procedures of the clinical sites.

Primary endpoint:

1. The proportion of subjects experiencing clinically significant local reactions including abscesses, hematoma formation or foreign body granuloma formulation, at the site of TachoSil application from the start of surgery up to 36 months post-surgery, as detected through routine imaging examinations (X-ray, ultrasound, CT, MRI or intraoperative detection or physical examination).

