Clinically significant reactions are defined as those that, in the investigator's opinion, require surgical re-intervention (e.g., relaparotomy, re-laparoscopy) and/or medical treatment due to signs and symptoms, as well as an impairment of organ function, which can be attributed to the product, local application changes at the site of product application noted during surgery or limitation or impairment of organ function noted during physical examination, reported by the patient or detected by abnormal imaging findings

Secondary endpoints:

1. The proportion of subjects experiencing clinically significant tissue adhesions detected from the start of surgery up to 36 months post-surgery, as detected through routine imaging tests such as X-ray, ultrasound, computed tomography, magnetic resonance imaging or relaparotomy or intraoperative detection or physical examination.

Clinically significant reactions are defined as those that, in the investigator's opinion, require surgical re-intervention (e.g., relaparotomy, re-laparoscopy) and/or medical treatment due to signs and symptoms, as well as an impairment of organ function, which can be attributed to the product, local application changes at the site of product application noted during surgery or limitation or impairment of organ function noted during physical examination, reported by the patient or detected by abnormal imaging findings.

2. Proportion of subjects experiencing at least one AESI during the perioperative period (from start of surgery until hospital discharge):

- Thrombotic and embolic events
- Postoperative bleeding at surgical site and at the site of application of the investigational medicinal product
- Allergic reactions / Immediate hypersensitivity reactions
- Other surgical related infections at the site of application of the investigational medicinal product

3. Proportion of subjects experiencing at least one AE related to the use of the study product in the period from the start of surgery up to 36 months post-surgery.

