10.2 SETTINGS

The study will include approx. 4 sites or more, if required (Table 1). Estimated total number of recruited patients is 66. Based on feasibility assessments, approximately 66 patients are expected to qualify for the study and undergo surgery. All patients who undergo surgery will be included in the analysis. An anticipated dropout rate is 10%. Finally, number of subjects eligible for analysis: sample size is expected to be at least 60. The prospective recruitment of patients, by enrolling patients who have planned surgery and meet enrolment criteria will last for 12 months from the study start. All recruited patients will be followed up to 36 months after the date of the surgery.

Note: in emergency situation that requires acute surgery with TachoSil application, obtaining informed consent and including the patient in the study after surgery may be considered, if legal and ethical requirements are met.

The study population is paediatric patients undergoing a cardiovascular, hepatic or other solid organs surgery and polytrauma with injuries of blood vessels, parenchymal organs, lungs requiring the use of drugs for local haemostasis, tissue sealing when control of bleeding by standard surgical techniques (such as suture, ligature, clips or cautery) appeared to be ineffective or impractical.

PasTel

Data will be collected from the following age groups :

- Infants and toddlers (≥ 28 days - < 2 years) on the day of signing the ICF
- Children (≥ 2 years – < 12 years) on the day of signing the ICF
- Adolescents (≥ 12 years – less than 15 years) on the day of signing the ICF

Patient age analysis will be conducted throughout the study to ensure a proportional number of participants in each of the three age groups (if possible, approx. 33% per group). Ensuring an adequate number of participants in each age group will ensure that data are collected across a broad paediatric population to assess short- and long-term safety evaluation.

Inclusion/Exclusion criteria

The study population covers paediatric patients undergoing a cardiovascular, hepatic or other solid organs surgery, and polytrauma patients with injuries of blood vessels, parenchymal organs, lungs requiring the use of drugs for local haemostasis, tissue sealing when control of bleeding by standard surgical techniques (such as suture, ligature, clips or cautery) appeared to be ineffective or impractical (secondary haemostatic treatment).

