Data will be collected from the following age groups:

- Infants and toddlers (≥ 28 days - < 2 years) on the day of signing the ICF
- Children (≥ 2 years – < 12 years) on the day of signing the ICF
- Adolescents (≥ 12 years – less than 15 years) on the day of signing the ICF

Inclusion criteria

The following individuals are eligible to participate:

- Patients aged from ≥ 28 days to < 15 years on the day of signing the ICF.

Important Note: According to legal regulations in Poland, patients who are 18 years of age or older cannot be treated by paediatric surgeons. Therefore, only patients who are under 18 years of age by the end of the observation period will be included in the study.

- Patients who have planned a cardiovascular, hepatic or other solid organs surgery and polytrauma patients with injuries of blood vessels, parenchymal organs, lungs qualified for elective surgery
- Patients planned to have at least one TachoSil matrix applied (intraoperatively) and without the plan of application of any other products for local haemostasis at the place of TachoSil application will be qualified for the study.

Exclusion Criteria

The following individuals are not eligible to participate:

- they have known, recognized earlier congenital disorders of haemostasis such as haemophilia type A,B,C, Marfan syndrome, Rendu-Osler-Weber disease, congenital thrombocytopathies, e.g. Glanzmann's thrombasthenia, von Willebrand disease type 1,2,3, Fanconi's anaemia.

PasTel

- they have experienced severe coagulopathy defined as: INR >2.0, platelet count (PLT)<50 000 / mm³; APTT>60 seconds in the period from 7 days before to the day of surgery.
- they are hypersensitive to the active substance(s) or to any of the product excipients.
- female patients of childbearing potential: they are pregnant or want to become pregnant or those who do not use sufficient methods of contraception such as contraceptive implant, intrauterine coil and oral hormonal contraception.

The patient who, in the investigator's opinion, presents a known risk of being lost to follow-up during the 36-month follow-up period, based on the screening assessment.

The study period will be divided into enrolment phase and follow-up phase. Both study phases can last simultaneously.

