Enrolment phase: The duration of this study phase is set to be 12 months, starting from the commencement of the study at each individual site. The center will be able to start recruiting patients after obtaining, accepting and signing all necessary documents to conduct an observational study in accordance with the regulations of Polish law. The Sponsor will communicate the study start date to the sites through email and telephone contact. Patient enrolment will be carried out amongst those scheduled for upcoming surgeries.

Patients who are scheduled to undergo cardiovascular, hepatic, or other solid organ surgeries, as well as polytrauma with injuries to blood vessels, parenchymal organs, or lungs, will be identified by the designated Investigator during their routine visit to the study site. During this visit, the Investigator will discuss the study details with the patient and/or their legal representative and ask for their willingness to participate. If the patient meets the remaining inclusion/exclusion criteria, including the intraoperative application of at least one TachoSil patch, they will be enrolled in the study. It's important to note that the participating sites will use TachoSil as part of their routine clinical practice in the specified indications mentioned above. TachoSil itself is not considered an intervention in the study; its application during surgery is one of the inclusion criteria. The day on which informed consent is obtained will be considered a screening visit.

For all enrolled patients, they will continue following the routine procedures of the study site leading up to the day of surgery and throughout their hospital stay until discharge. The Investigator will perform safety assessments during the perioperative period, which includes the time from the day of surgery until discharge. These assessments will involve monitoring adverse events (AEs), adverse events of special interests (AESIs), vital signs (blood pressure, heart rate, temperature), and the analysis of relevant clinical laboratory variables as part of the routine procedure (morphology, INR, APTT).

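### The contraception-use exclusion, with no exception for girls who are not sexually active, leaves some under-15 girls out of the safety data of a non-interventional cohort without changing whether they receive TachoSil

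*Protocol*

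**What the plan says.** The exclusion criteria in Protocol sections 5 (Abstract) and 10.2 (Settings) cover "female patients of childbearing potential: they are pregnant or want to become pregnant or those who do not use sufficient methods of contraception". Both then give examples of acceptable methods; the full limb in 10.2 reads "those who do not use sufficient methods of contraception such as contraceptive implant, intrauterine coil and oral hormonal contraception". Neither place mentions abstinence or sexual inactivity, defines childbearing potential, or gives a reason for the rule.

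The surrounding text matters for how this works:

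- **Age:** eligibility is "Patients aged from ≥ 28 days to < 15 years on the day of signing the ICF".
- **Design (10.1):** "This is a prospective, multicentre, non-interventional, uncontrolled, observational, post-authorization cohort study".
- **Exposure (10.2, Enrolment phase):** "TachoSil itself is not considered an intervention in the study; its application during surgery is one of the inclusion criteria". Section 11 adds that patients' treatment is unaffected by the study.
- **Withdrawal (10.2, Follow-up phase):** a patient may be withdrawn if the investigator finds that the eligibility criteria are no longer met.
- **Coverage (10.2):** about one third of patients are sought in each of three age groups, if possible, so that the data span a wide paediatric population.
- **Selection bias:** section 10.9 names the haemostasis and coagulopathy exclusions but not this one. The checklist in Annex 2 (items 7.2 and 12.1.1) marks selection bias as not applicable, on the ground that recruits and the population of interest are the same.

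**The concern.** In an interventional trial, a contraception requirement limits exposure during pregnancy. Here the study does not decide exposure. A girl whom this clause keeps out can still receive the patch in routine care; what changes is that her outcomes are not recorded. The rule therefore narrows who is observed, not who is treated.

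Among girls under 15, using no contraception may simply mean not being sexually active. With no exception for that, entry to the oldest age band (12 to under 15 years) depends, for girls of childbearing potential, on contraceptive use. No stated study purpose calls for that filter. At stake is whether the adolescent results describe adolescent girls as they are treated in practice. Section 8 says the EU paediatric indication runs from 1 month to 18 years, so these girls belong to the population that the study is meant to inform.

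The withdrawal rule could extend the effect beyond enrolment. A girl enrolled before menarche, including one from the 2 to under 12 band, may come under the clause during the 36 months over which the primary endpoint is counted.

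**Working it through.** **The plan's own figure.** Section 10.2 expects 66 recruited, 10% dropout and at least 60 analysable. 66 × (1 − 0.10) = 59.4, or about 60. This reproduces, and the point does not disturb it.

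**Size of the adolescent group.** About one third of 66: 66 × 1/3 = 22.

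**Places affected.** Treat the 22 as the adolescent places that would be filled if the limb were absent. Then

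places going to other patients = 22 × f × p × (1 − c),

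where f is the share of girls, p the share of girls of childbearing potential (taken as post-menarchal) and c the share of those using a qualifying method. The documents give none of these three, so all are assumptions. With f = 50%, there are 22 × 0.5 = 11 girls.

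| p | Girls under the clause (11 × p) | c = 0% | c = 10% | c = 30% | c = 60% |
|---|---|---|---|---|---|
| 30% | 3.3 | 3.3 | 3.0 | 2.3 | 1.3 |
| 60% | 6.6 | 6.6 | 5.9 | 4.6 | 2.6 |
| 90% | 9.9 | 9.9 | 8.9 | 6.9 | 4.0 |

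The range is 1.3 to 9.9 places: 6% to 45% of 22, or 2% to 15% of 66. With f = 40% (8.8 girls), it is 8.8 × 0.3 × 0.4 = 1.1 to 8.8 × 0.9 = 7.9.

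**Effect on total N.** None is shown. Sections 10.2 and 10.5 describe the 66 as patients expected to qualify, and 10.5 continues recruitment until the planned number is reached. Boys, girls not yet of childbearing potential and contraceptive users would fill the places.

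**Passages side by side.**

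- The exclusion makes entry depend on contraceptive use. The checklist says that recruits do not differ systematically from the population of interest. For girls of childbearing potential, both cannot hold.
- Section 10.9 accepts that the eligibility criteria may produce selection bias, while the checklist calls it not relevant. These disagree already, and neither mentions this clause.
- The emergency note in 10.2 allows consent and inclusion after surgery. The criterion would then be applied to a girl who has already been exposed, where it can only remove data.

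**The case against.** The strongest reply is that the effect is small and largely unquantified. Several parts of that stand.

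- The words introducing the three methods make them examples. An investigator could accept another method as sufficient, so the text does not strictly require an implant, coil or pill. That softens the rule, but it leaves the judgement undefined across sites and still gives no exception for a girl who uses nothing.
- A reader might infer that the clause removes most post-menarchal girls. That holds only if fewer than half use a qualifying method, and the documents give no such rate.
- A reader might infer that the girls admitted are mainly hormone users, which would confound "Thrombotic and embolic events", an AESI in secondary endpoint 2. The documents do not support this. They describe only the oral method as hormonal and say nothing about contraception and thrombosis. With c at 10%, only 0.3 to 1.0 such girls are admitted. At 60%, 2.0 to 5.9 are admitted, but then the clause no longer removes most. The study is uncontrolled and descriptive, and concomitant medication is recorded throughout.
- A reader might infer a contradiction with the one-third target. That target is by age only and qualified by feasibility, so boys and pre-menarchal girls can meet it.
- Section 10.9 acknowledges selection bias from the criteria in general terms.
- The sponsor may have a reason for a pregnancy-related rule that the protocol does not state.

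None of this answers the central point: the rule, as worded, drops girls from observation without affecting their treatment, and the protocol neither justifies nor acknowledges it.

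**Conclusion.** The point holds as a defect of representativeness in one subgroup. Read literally, a girl of childbearing potential who uses no contraception is ineligible for a cohort that merely observes her routine care, and a girl who reaches menarche during follow-up could be withdrawn. This runs against the aim of broad paediatric coverage and against the checklist's selection-bias answers.

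The size is roughly 1 to 10 of about 22 adolescent places, on assumed values for the share of girls, childbearing potential and contraceptive use. Total N, the dropout arithmetic and the one-third age target are not shown to be affected. The withdrawal effect is a possibility, because the rule is permissive, and it cannot be sized from the documents. The change is worth making because it is almost free, and data collection is not due to start until 3Q 2026.

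**What to change.** 1. In sections 5 and 10.2, reconcile the criterion with the non-interventional design by removing the contraception-use limb as a condition of data collection. At the least, state that girls who are not sexually active are not excluded by it.
2. In the withdrawal paragraph of 10.2, state that withdrawal for no longer meeting the criteria does not apply to this limb.
3. If any part is kept, give the reason, name it in 10.9 as a source of selection, and correct checklist items 7.2 and 12.1.1 and their comments.

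The rule on pregnancy itself is for the sponsor to decide.

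The cost is wording in a protocol amendment, with no new procedure or data item. The downside is that a pregnancy could occur during follow-up; it would be handled by ordinary safety reporting.

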Follow-up phase: The study phase is scheduled to last for up to 36 months following the date of surgery for each enrolled patient. There are six planned follow-up visits: one at 1 month (\pm 15 days) after surgery, another at 3 months (\pm 15 days), a third at 6 months (\pm 15 days), and a fourth, fifth and sixth visits at 12, 24 and 36 months (\pm 30 days) post-surgery, respectively. However, to minimize stress for patients and caregivers associated with the study and the surgical intervention itself, the number and frequency of follow-up visits during the observation period can be align with the routine follow-up procedures of the clinical sites.

The follow-up visits can be conducted in person at the study site if such visits are routinely performed, or they can take the form of telephone interviews with the patient and/or patient

PasTel

legal representative conducted by the Investigator. In both cases eCRF should be completed with all collected and required by Protocol data.

Patients have the right to discontinue their participation in the study at any time and for any reason, whether specified or unspecified.

Furthermore, a patient/legal representative (if applicable) may be withdrawn from the study if the Investigator determines that the patient no longer meets any of the inclusion/exclusion criteria.

Lost-to-follow-up (LTFU)

To ensure the smooth progress of the PasTel study, it is crucial to minimize the occurrence of lost-to-follow-up (LTFU). Loss-to-follow-up refers to patients and/or their legal representative who, at some point during the study, cannot be reached for further follow-up procedures, resulting in an unknown status and the inability to collect important long-term information, including adverse events. On the other hand, "dropout" refers to patients who voluntarily withdraw from the study, with their health status known upon departure.

To minimize lost-to-follow-up, the following follow-up process will be implemented: If a study participant (or their legal representative) does not respond to the initial telephone contact, up to two reminder calls will be made. If there is still no response after three phone calls, the participant will be sent an email or certified letter. The overall objective is to keep the loss-to-follow-up rate below 10 %. Based on the Corza Medical experience and Feasibility analysis, it is anticipated that the final LTFU will be approximately 10 %.

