 - type and date and time of surgery
 - patient's discharge details
- Adverse Events evaluation including treatment of AEs
- Adverse Events of Special Interest evaluation including treatment of AESIs
- Comorbidities and their evaluation for the assessment of adverse events (AEs / AESI)
- TachoSil usage related data:
 - exposure/dose/application time (size and number of patches applied)
 - repeated application
 - treatment not effective/other treatment required
 - Batch number, expiration date and size of all TachoSil matrices used
 - The wound condition and application of the TachoSil matrix will be assessed and collected. The following wound data will be assessed and collected: wound location, amount of blood in the wound assessed by the surgeon. The following TachoSil matrix data will be collected: TachoSil matrix size, and application method (dry, pre-moistened).
- Concomitant medication(except drugs used for anaesthesia)
 - Specific treatments, such as: ECMO (extracorporeal membrane oxygenation), hypothermia, ECC (extracorporeal circulation), MiECC (minimal invasive systems for extracorporeal circulation),
- Vital signs (as per each site's standard of care as blood pressure, body temperature, and heart rate), if available
- Laboratory data (as per each site's standard of care such as: blood count, C-reactive protein [CRP], International Normalized Ratio[INR], Activated Partial Thromboplastin Time [APTT]),if available

Hospital Discharge Data

At the time of discharge following information should be collected and enter into eCRF:

PasTel

- Concomitant therapies updates
- Adverse Events evaluation including treatment of AEs
- Adverse Events of Special Interest evaluation including treatment of AESIs
- Comorbidities and their evaluation for the assessment of adverse events (AEs / AESI)
- Granuloma occurrence and Tissue adhesions and other clinically significant events for the endpoint
- Vital signs (as per each site's standard of care as blood pressure, body temperature, and heart rate), if available
- Laboratory data (as per each site's standard of care such as: blood count, C-reactive protein [CRP], International Normalized Ratio[INR], Activated Partial Thromboplastin Time [APTT]),if available

Follow-up Visits/Contacts

At the time of Follow Up Visits/Contacts following information should be collected and enter into eCRF:

- Concomitant therapies updates
- Adverse Events evaluation including treatment of AEs

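### The follow-up text lets an investigator withdraw a child over eligibility after TachoSil has been applied, and one open-ended criterion, hypersensitivity, is also a study outcome

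*Protocol*

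**What the plan says.** Protocol section 10.2 (Settings), under the follow-up phase, provides that a patient or legal representative "may be withdrawn from the study if the Investigator determines that the patient no longer meets any of the inclusion/exclusion criteria". The decision is the investigator's. The sentence sets no time limit, does not separate children who have received a patch from those who have not, and does not provide for continued safety contact after withdrawal.

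The eligibility list in the same section includes these items:

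- Hypersensitivity, as an exclusion: "they are hypersensitive to the active substance(s) or to any of the product excipients". No time window is given.
- Pregnancy and contraception, as an exclusion for female patients of childbearing potential: "they are pregnant or want to become pregnant", or not using sufficient contraception. No time window is given.
- Severe coagulopathy, as an exclusion with a window that closes at surgery: "APTT>60 seconds in the period from 7 days before to the day of surgery".
- Other local haemostatics, as an inclusion criterion about intention: "without the plan of application of any other products for local haemostasis at the place of TachoSil application".

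Section 10.1 lists "Allergic reactions / Immediate hypersensitivity reactions" among the perioperative AESIs that form secondary endpoint 2. It also commits the study to following all enrolled patients for up to 36 months. Sections 10.2 and 10.7 keep all operated patients, or all enrolled patients with at least one application, in the analysis. Section 10.3 asks for adverse events, AESIs, granuloma and adhesion data at premature discontinuation only if possible, and schedules nothing afterwards.

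**The concern.** Eligibility criteria normally decide who enters a cohort. Here they can also decide who continues to be observed after exposure. Where a criterion can be met because of something the product did, an outcome becomes a permitted reason to stop looking for further outcomes.

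TachoSil is applied during surgery, and section 10.3 states that it stays in the wound until it degrades. Withdrawal therefore stops no treatment. It stops only data collection, in a study whose stated main purpose is long-term or delayed safety. An immediate hypersensitivity reaction would occur early, so nearly the whole 36-month window could be lost for that child. The results at stake are the primary endpoint (clinically significant local reactions to 36 months), secondary endpoint 1 (adhesions to 36 months) and secondary endpoint 3 (related adverse events to 36 months).

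**Working it through.** **1. How the rule is read.** Taken literally, the sentence is awkward, because an enrolled child should meet no exclusion criterion. I read it as covering a child who stops satisfying an inclusion criterion or comes to meet an exclusion criterion.

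**2. Which criteria can change after the patch is applied** (sections 10.1 to 10.3):

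| Criterion | Can it be triggered after application? | Is it a study outcome? |
|---|---|---|
| Hypersensitivity to the product | Yes, no time window | Yes, AESI in secondary endpoint 2 |
| Pregnancy / contraception | Yes, no time window | No |
| Severe coagulopathy | Not after the day of surgery | Not a listed AESI |
| No other local haemostatic planned | No, it concerns the plan | Failure is recorded as "treatment not effective/other treatment required" |
| Age | No, fixed on the day of consent | No |
| Risk of loss to follow-up | No, fixed at screening | No |

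Only hypersensitivity is both open-ended and an outcome. Pregnancy/contraception widens the reach of the rule but does not make the loss depend on an outcome.

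**3. The planned numbers.** Section 10.2 gives 66 recruited, 10% dropout and at least 60 for analysis. 66 × 0.90 = 59.4, so the figure is reproduced to rounding. The same section defines dropout as voluntary withdrawal and loss to follow-up as being unreachable. Withdrawal by the investigator is neither, so any such withdrawals come on top of the 10%.

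**4. Effect on precision.** With zero events, the exact two-sided 95% upper limit is 6.0% for 0/60 and 6.7% for 0/53, that is, after seven further losses. Precision is barely affected.

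**5. Effect on the estimate.** Sections 10.2 and 10.7 keep the withdrawn child in the denominator. If the endpoint is reported as a simple proportion, an event after withdrawal is counted as no event. The shortfall is (unseen events)/66, and 1/66 = 1.5 percentage points. For illustration, assume 66 exposed and 3 events observed (3/66 = 4.5%):

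- 1 unseen event: (3 + 1)/66 = 6.1%
- 3 unseen events: (3 + 3)/66 = 9.1%

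If withdrawn children are instead censored, as in a cumulative incidence estimate, the result is biased downwards only if their later risk is higher than that of the children who remain. The protocol gives no data on this.

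**6. How many children.** The documents do not say. The nearest figure is in Table 4 (section 8): immunological events in 4/36 TachoSil children, or 11.1% (exact 95% CI 3.1% to 26.1%). Applied to 66 this is 66 × 4/36 = 7.3. It would be a count of reactors only if every such event were hypersensitivity to the product, which the protocol does not say. The comparator rate in the same table is 1/9, also 11.1%.

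**The case against.** The strongest defence is that the sentence has an ordinary purpose. Section 10.2 makes intraoperative application of at least one patch part of eligibility, and that can be settled only at surgery. Table 5 checks inclusion and exclusion criteria at screening and surgery and at no follow-up visit. The natural use is then a child who gave consent but received no patch. This stands as an account of likely practice, and it determines where the cut-off belongs. It does not settle the wording, which appears under follow-up and reaches exposed children too.

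It can also be said that safeguards exist. Events up to withdrawal stay in the analysis, data are sought at discontinuation, section 12 requires each adverse event to be followed through its course, and missing-data handling is left to the SAP. This stands for the acute reaction, which will be counted. It does not help with a granuloma or adhesion that first appears months later in a child no longer contacted, because analysis cannot recover an event nobody looked for.

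A reader might infer more than the documents support:

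- **That coagulopathy or patch failure leads to withdrawal.** The coagulopathy window closes on the day of surgery. The haemostatic criterion concerns intention, and failure is itself a recorded variable, which implies that those children stay in.
- **That reactors are removed as a rule.** The sentence is permissive, and no follow-up visit rechecks eligibility.
- **That about 7 children would be lost.** This treats every immunological event in Table 4 as product hypersensitivity. Section 8 attributes no serious adverse event to treatment and describes the mild or moderate events as unrelated. A raised later risk in reactors would be a further assumption without support.

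**Conclusion.** The point holds in a limited form. As worded, section 10.2 allows an exposed child's follow-up to end because of a hypersensitivity reaction that is itself a study outcome, or because pregnancy or contraception status has changed. This contradicts the section 10.1 commitment on follow-up, and nothing in section 10.3 makes good the lost time.

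The possible error in the 36-month proportions is downward, which is the unfavourable direction for a safety study. It amounts to 1.5 percentage points for each unseen event among 66 children. The number affected is unknown and probably small, and the effect on precision is minor. The conclusion rests on two assumptions: that the sentence is read as in step 1, and that endpoints are reported as simple proportions of exposed children. Under censoring, the downward direction would also require withdrawn children to be at higher risk.

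**What to change.** In section 10.2, replace the withdrawal sentence with text to this effect: eligibility-based withdrawal applies only to children who have not received a TachoSil patch. Every enrolled child with at least one patch stays in safety follow-up until 36 months, death, loss to follow-up or withdrawal of consent. Any later change in an eligibility criterion is recorded and is not a reason for withdrawal.

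The cut-off should be application of the patch and not the start of surgery. Operated children who received no patch can then still be withdrawn, which agrees with the section 10.7 analysis population.

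The cost is one short protocol passage and no visits beyond those already scheduled. It is best made before data collection starts, planned for 3Q 2026, because follow-up that was not collected cannot be restored at analysis.
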